### 9.2 Demographics and Subject Disposition

Subject disposition will be listed. The demographic variables age, sex, race, ethnicity, country of enrolment, screening HbA1c, screening fasting blood glucose, screening fasting C-peptide, duration of T1DM, site ID, body weight, height, and body mass index will be summarized and listed.

In addition, the following dosing data will be listed and summarized:

- Insulin dose at screening (stored in the concomitant dataset) for basal, bolus, and total.
- Dose finding dose for the MMTT (the dose administered for the dose finding and the dose selected after the dose finding on Day 1, Period 1 which will be used for all MMTT, and is the dose selected on the exposure dose finding page).

### 9.3 Pharmacokinetic Analyses

#### 9.3.1 Pharmacokinetic Parameter Estimation

Patients who complete at least 1 MMTT and have measurable insulin concentrations will be included in the analysis dataset for the PK analyses. Pharmacokinetic analyses will be conducted using standard noncompartmental methods of analysis (Phoenix® version 6.3 or above) on a computer that meets or exceeds the minimum system requirements for these programs. It is possible that other validated equivalent PK software programs may be utilised if appropriate, warranted and approved by global PK management. The version of any software used for the analysis will be documented, and the program will meet the Lilly requirements of software validation.

Serum insulin lispro and plasma or serum insulin aspart concentrations will be used to calculate several PK parameters, including time to early half-maximal drug concentration (early 50%  $t_{max}$ ), time to late half-maximal drug concentration (late 50%  $t_{max}$ ), maximum observed drug concentration ( $C_{max}$ ), time to maximum observed drug concentration ( $t_{max}$ ), AUC from time zero to time  $t$ , where  $t$  is the last time point with a measurable concentration (AUC[0- $t_{last}$ ]), AUC(0-30min), AUC from time 0 to 1 hour (AUC[0-1h]), AUC from time 0 to 7 hours (AUC[0-7h]) and AUC from time zero to infinity (AUC[0- $\infty$ ]). Additional partial AUCs may be computed as necessary, such as AUC from time 0 to 2 hours (AUC[0-2h]), AUC from time 3 to 7 hours (AUC[3-7h]), and onset of appearance of serum lispro/aspart in the blood.

In addition, a graphical comparison of the “normal” insulin secretory response using the endogenous insulin levels following the MMTT from healthy subjects to the insulin lispro/aspart profile following these insulin analogues (LY900014, Humalog, FIASP or NovoRapid) in patients with T1DM will be performed. Additional analysis may be performed, if needed.

Although attempts will be made to adhere to the scheduled collection times, it is recognised that situations arise that may compromise sample collection at the scheduled times. Parameters will be individually calculated for each patient based on actual collection times and presented by summary statistics.

Study results may be pooled with the results of other studies for population PK analysis purposes to avoid issues with post hoc analyses and incomplete disclosures of analyses.

#### 9.3.2 Pharmacokinetic Statistical Inference

Patients who did not keep identical prandial insulin doses for the MMTTs across all periods will be excluded from the statistical analysis of the PK parameters.

The PK time parameters (early 50%  $t_{max}$ , late 50%  $t_{max}$  and  $t_{max}$ ) in the original scale will be analysed by the mixed-effect model that includes treatment (LY900014, Humalog, FIASP, NovoRapid), treatment sequence and period as fixed effects and patient within sequence as a random effect. Least-squares means (LSmeans), treatment differences in LSmeans and the corresponding 95% CIs for the treatment differences will be estimated from the model. The p-value on the difference between LSmeans will be used to determine statistical significance.

The treatment ratios and 95% CIs for the ratios will be calculated using Fieller's theorem (Chow and Liu 2009).

Example SAS code:

```
proc mixed data=pk;  
class patient period treatment;  
model logpk = treatment period / ddfm=kr alpha=0.05;  
random patient;  
lsmeans treatment;  
run;
```

Log-transformed AUCs,  $C_{max}$  for insulin lispro/aspart may be evaluated to estimate geometric means, ratios of geometric means and their corresponding 95% CIs using the same mixed-effect model as PK time parameters.

Statistical significance will be achieved when the p-value for a test is less than 0.05. The primary comparison will be of LY900014 to Humalog. The following comparison will also be performed. No multiplicity test adjustment will be made for these comparisons.

- LY900014 versus FIASP
- LY900014 versus NovoRapid
- Humalog versus NovoRapid

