5.4. Scientific Rationale for Study Design

This study has a 4-period crossover design to reduce the variability of insulin PK and PD as each patient will serve as his/her own control. Also, the total number of patients needed with a crossover design is less than the number needed with a parallel group design. A maximum duration of approximately 6 weeks is allowed for patients to complete all 4 assigned periods to minimise the risk of insulin resistance/changes in mean glycaemic control during the study.

This study is being conducted in patients with T1DM, as this is the target population for the study drugs. Additionally in patients with T1DM there is no interference of endogenous

insulin. A healthy subject cohort is being included to characterise the normal physiological insulin secretory response to a single standardised MMTT.

Randomisation and blinding are used to avoid bias introduced through an association between allocation order of study drugs and patient characteristics. The Lilly clinical pharmacologist (CP)/Lilly study team will be unblinded.

In each study period, patients will undergo a run-in period before the MMTT using a variable insulin and glucose IV infusion. This run-in period will allow for improved comparability of the postprandial glucose response to a mixed meal after treatment with LY900014, Humalog, FIASP, and NovoRapid when administered immediately before the start of the meal. This run-in aims to achieve similar preprandial glucose levels for all patients before the start of the standardised test meal and thereby reduces the variability of the postprandial glucose response. Insulin glulisine has been chosen for IV optimisation of blood glucose during the run-in because it does not cross-react with either the insulin lispro- or insulin aspart-specific assay used for the PK analysis.

Under this design, if 2 periods occur on consecutive days, the interval between the last bolus on the first day and the first bolus on the second day is much longer compared to the length of time that the treatment (LY900014, Humalog, FIASP or NovoRapid) lasts in the bloodstream; therefore, no carryover effect is expected. This enables PK and PD data from the breakfast meal tests of each period to be analysed independently and separately.

At least 21 hours between the doses of study drug allows for a complete washout of study drug administered with the MMTT and glucose response and prevents carryover effects.

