10.1. Sample Size Determination

An initial 74 patients with T1DM may be enrolled so that approximately 64 patients complete the study. Sixty-four completing patients will provide at least 95% power to demonstrate a 2-fold increase in the serum insulin lispro AUC from time 0 to 30 minutes (AUC[0-30min]) between LY900014 and the Humalog. Testing will be done at an alpha level of 0.05 with a 2-sided confidence interval (CI). The sample size will also provide greater than 95% power to demonstrate a 35% reduction of early 50% t_{max} between LY900014 and Humalog. The estimated standard deviation of within-subject difference on the log scale is 0.35 for AUC(0-30min) and 0.3 for early 50% t_{max} , according to an analysis of internal Lilly data (Study I8B-FW-ITRG) for LY900014 and Humalog administered in a repeat-dose study.

With this sample size, there is more than 95% power to detect a 40% reduction in postprandial glucose incremental area under the baseline subtracted glucose concentration versus time curve from time 0 to 1 hour (Δ AUC[0-1h]) between LY900014 and Humalog. With similar assumptions, the study is also adequately powered for the comparison between LY900014 and NovoRapid.

With 64 completing patients, there is more than 95% power to detect a 20% reduction of early 50% t_{max} between LY900014 and FIASP. In addition, there is approximately 80% power to demonstrate a 25% reduction in postprandial glucose incremental AUC from time 0 to 1 hour between LY900014 and FIASP. The power calculation is based on published results of FIASP studies and internal Lilly data.

Patients who are randomised but drop out before completing assigned treatment may be replaced to ensure that approximately 64 patients complete the study.

For the healthy cohort, 12 non-diabetic healthy subjects will be evaluated for their glucose and insulin secretory response to the MMTT. No treatment will be provided for this cohort. The sample size for the healthy cohort was chosen to provide sufficient data in order to evaluate the objectives of the study, and is not intended to achieve any a priori statistical requirements.

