## 7. SAMPLE SIZE JUSTIFICATION

An initial 74 patients with T1DM may be enrolled so that approximately 64 patients complete the study. Sixty-four completing patients will provide at least 95% power to demonstrate a 2-fold increase in the serum insulin lispro AUC from time 0 to 30 minutes (AUC[0-30min]) between LY900014 and the Humalog. Testing will be done at an alpha level of 0.05 with a 2-sided confidence interval (CI). The sample size will also provide greater than 95% power to demonstrate a 35% reduction of early 50%  $t_{max}$  between LY900014 and Humalog. The estimated standard deviation of within-subject difference on the log scale is 0.35 for AUC(0-30min) and 0.3 for early 50%  $t_{max}$ , according to an analysis of internal Lilly data (Study I8B-FW-ITRG) for LY900014 and Humalog administered in a repeat-dose study.

With this sample size, there is more than 95% power to detect a 40% reduction in postprandial glucose incremental area under the baseline subtracted glucose concentration versus time curve from time 0 to 1 hour ( $\Delta$ AUC[0-1h]) between LY900014 and Humalog. With similar assumptions, the study is also adequately powered for the comparison between LY900014 and NovoRapid.

With 64 completing patients, there is more than 95% power to detect a 20% reduction of early 50%  $t_{max}$  between LY900014 and FIASP. In addition, there is approximately 80% power to demonstrate a 25% reduction in postprandial glucose incremental AUC from time 0 to 1 hour between LY900014 and FIASP. The power calculation is based on published results of FIASP studies and internal Lilly data.

Patients who are randomised but drop out before completing assigned treatment may be replaced to ensure that approximately 64 patients complete the study.

For the healthy cohort, 12 non-diabetic healthy subjects will be evaluated for their glucose and insulin secretory response to the MMTT. No treatment will be provided for this cohort. The sample size for the healthy cohort was chosen to provide sufficient data in order to evaluate the objectives of the study, and is not intended to achieve any a priori statistical requirements.

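### Does pooling residual variance over lispro and aspart periods undermine the confidence interval for the primary LY900014 versus Humalog AUC(0-30min) ratio?

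*SAP*

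**What the plan says.** SAP section 9.3.2 and Protocol section 10.3.2.2 describe one mixed model for the PK parameters: a four-level treatment factor (LY900014, Humalog, FIASP, NovoRapid), sequence and period as fixed effects, and patient within sequence as the random effect. The time parameters are analysed untransformed. Log AUCs and Cmax values "for insulin lispro/aspart may be evaluated to estimate geometric means, ratios of geometric means and their corresponding 95% CIs using the same mixed-effect model" that serves those time parameters. LY900014 versus Humalog is the primary comparison.

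The SAP adds example SAS code. Its model line is "model logpk = treatment period / ddfm=kr alpha=0.05" and its only random statement is "random patient". Nothing groups the residual variance by treatment or by molecule.

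Table ITSL.1 of the protocol names AUC(0-30min) and early 50% tmax as the primary endpoints. SAP section 7 and Protocol section 10.1 give an SD of the within-subject difference of log AUC(0-30min) of 0.35, obtained "according to an analysis of internal Lilly data (Study I8B-FW-ITRG) for LY900014 and Humalog administered in a repeat-dose study". No SD is given for aspart AUC(0-30min).

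**The concern.** Lispro and aspart are different analytes. Protocol section 5.4 explains the choice of glulisine for the run-in by noting that "it does not cross-react with either the insulin lispro- or insulin aspart-specific assay used for the PK analysis", so two separate assays are in use, and the aspart matrix may be plasma or serum. With one residual variance, half of the information on the error of the LY900014 versus Humalog contrast comes from periods with neither product. If aspart is less variable than lispro, the interval is too short and the type I error exceeds 5%. If it is more variable, or if patients differ in how they respond to the two molecules, the interval will tend to be too long. The power statement rests on lispro variability alone, so the planned interval and the sample size appear to use different variances. The nominal 95% level of a primary endpoint's interval would be at stake.

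**Working it through.** **Inputs from the documents.** n = 64 completers; 2-fold increase, ln 2 = 0.693; two-sided alpha 0.05; SD of the within-subject difference 0.35 (SAP section 7, Protocol section 10.1).

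**Assumed, because not given.** Ratio k of aspart to lispro residual SD, from 0.5 to 2; patient-by-molecule SD tau, 0 or 0.2.

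**1. The plan's own power figure.** SE = 0.35/√64 = 0.04375. Effect/SE = 0.693/0.04375 = 15.8. Paired t power on 63 df is above 99.9%, which agrees with the stated figure of at least 95%. Six completers would reach 95%. With 64, power falls to 95% only if the SD of the difference is about 1.51, more than four times 0.35.

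**2. What pooling does to the interval.** Lispro residual SD per period = 0.35/√2 = 0.247. In a balanced four-treatment crossover with tau = 0, the pooled residual variance is 0.247² × (1 + k²)/2, so the reported SE is the true SE times f = √((1 + k²)/2). Residual df = 256 − 64 − 3 − 3 = 186, t = 1.973. Coverage = 2Φ(1.973 × f) − 1; log half-width = 1.973 × f × 0.04375. The last column is from 4,000 simulated trials per setting (64 patients, Williams sequences assumed).

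| k | Aspart SD | f | Interval around a ratio of 2 | Coverage, formula | Coverage, simulated |
|---|---|---|---|---|---|
| 0.5 | 0.124 | 0.791 | 1.87 to 2.14 | 88.1% | 88.2% |
| 0.67 | 0.166 | 0.851 | 1.86 to 2.15 | 90.7% | 90.4% |
| 1 | 0.247 | 1 | 1.84 to 2.18 | 95.2% | 94.9% |
| 1.5 | 0.371 | 1.275 | 1.79 to 2.23 | 98.8% | 98.8% |
| 2 | 0.495 | 1.581 | 1.75 to 2.29 | 99.8% | 99.9% |

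A paired lispro-only interval (t = 1.998 on 63 df) has half-width 0.0874, that is 1.83 to 2.18, and covers about 95% throughout. Pooled coverage stays between 92.5% and 97.5% for an aspart SD of about 0.20 to 0.31.

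**3. Patient-by-molecule variance.** This adds 2 × tau²/3 to the pooled residual variance. With tau = 0.2, coverage is 96.3%, 98.2% and 99.7% at aspart SDs of 0.15, 0.247 and 0.40, so the interval is conservative.

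**4. Could the conclusion change?** For an interval around 2 to reach 1, f would have to be 0.693/(1.973 × 0.04375) = 8.0. Then k = √(2 × 8.03² − 1) = 11.3, an aspart SD of 11.3 × 0.247 = 2.8. Nothing in the documents points to anything of that order.

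**5. Is there evidence of unequal variance?** The documents give no aspart variance and no sign of a patient-by-molecule effect. What the design fixes speaks, if anything, for similar variability: the same patients, the same unit dose for every insulin (Protocol sections 5.1.1 and 7.2.1), the same test meal (6.3.1), and assays described as validated for both analytes (9.5.1).

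**The case for a change.** The strongest case for the concern is that nothing in the documents states or justifies equal variance across molecules and assays, that no lispro-only sensitivity analysis is planned, and that one would be cheap: 60 instead of 186 residual df widens the interval by 1.4% (t of 2.000 against 1.973). These facts stand, and so does the coverage arithmetic for any assumed k. At k = 0.5 the type I error would be about 12%, which would matter if the true effect were near zero.

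They do not amount to an error. Equal residual variance is the working assumption of the usual crossover model and is seldom proved in a protocol. Under it, the pooled variance and the planning variance estimate the same quantity, so there is no mismatch with the power basis; a planning SD from another study need not mirror the analysis estimator in any case. The early 50% tmax analysis uses the same four-insulin model, so an argument confined to AUC and Cmax would leave the two primary endpoints on different models without a reason. Nor is every alternative safer. Separate residual variances by molecule with only a patient intercept gave an interval 37% wider than lispro-only in one simulated setting (tau = 0.2, aspart SD 0.15, between-patient SD 0.3, all assumed), against 5% wider for the pooled model.

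Protocol section 5.4 does say "This enables PK and PD data from the breakfast meal tests of each period to be analysed independently and separately", but that sentence concludes an argument that no carryover is expected between consecutive days. It does not call for separate models by molecule.

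The example code is a sketch. It omits the sequence term named in the text and requests no treatment differences or confidence limits, so the pooling follows from the model description and not from a coded interval.

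Two wording points remain. Section 9.3.2 says log AUCs *may* be evaluated, which is loose for a primary endpoint; but Table ITSL.1 makes AUC(0-30min) primary and SAP section 7 says it will be tested, so the intention is not in doubt. The 0.05 rule is also covered: Protocol section 10.3 applies it to all tests unless otherwise noted, and in SAP section 9.3.2 the general significance sentence directly follows the AUC and Cmax paragraph.

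**Conclusion.** The concern does not hold. The plan implies one residual variance over four insulins, and the 0.35 is a lispro figure; both readings are correct. But the loss of coverage depends wholly on an aspart SD and a patient-by-molecule SD that the documents do not give, and its direction cannot be told. With equal SDs and no patient-by-molecule variance the plan is correct as written, with coverage of 95%. Even at the extremes examined (k from 0.5 to 2, tau = 0), the interval around a 2-fold ratio only moves between 1.87 to 2.14 and 1.75 to 2.29, power stays above 99.9%, and the point estimate is unaffected. Restricting the primary contrast to the lispro periods is a defensible modelling preference, not the correction of a defect. This rests on balanced data from about 64 completers and on a true effect of roughly the planned size.

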9.5. Pharmacokinetics

At the visits and times specified in the Schedule of Activities (Section 2), venous blood samples will be collected to determine the serum concentrations of insulin lispro and plasma or serum concentrations of insulin aspart in patients with T1DM. Instructions for the collection and handling of blood samples will be provided by the sponsor. The actual date and time (24-hour clock time) of each sampling will be recorded.

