9.5.1. Bioanalysis

Samples will be analysed at a laboratory approved by the sponsor and stored at a facility designated by the sponsor.

Serum concentrations of insulin lispro will be measured using a validated CCI [REDACTED] method specific for insulin lispro at a laboratory approved by the sponsor.

Plasma or serum concentrations of insulin aspart in patients with T1DM will be measured using a validated CCI [REDACTED] method specific for insulin aspart at a laboratory approved by the sponsor.

Bioanalytical samples collected to measure investigational product concentrations will be retained for a maximum of 1 year following last patient or subject visit for the study.

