10.3. Statistical Analyses

Statistical analysis of this study will be the responsibility of Eli Lilly and Company or its designee.

Primary statistical analyses of PK and PD parameters for the cohort of patients with T1DM will be conducted on the set of patients who complete all treatment periods with identical prandial insulin doses for the MMTTs during the study, as the PK parameters and PD response is dependent on the insulin dose which is individualised for each patient. Supportive analyses may be done on the key parameters for the patients who complete at least 2 treatment periods.

Any change to the data analysis methods described in the protocol will require an amendment only if it changes a principal feature of the protocol. Any other change to the data analysis methods described in the protocol and the justification for making the change will be described in the study results.

Safety analyses will be conducted on the set of patients receiving at least 1 dose of the study drug to which they are randomised, regardless of whether or not they completed all protocol requirements.

Unless otherwise noted, all tests of treatment effects will be conducted at a 2-sided alpha level of 0.05, and CIs will be calculated at 95%, 2-sided. No multiplicity test adjustment will be made for secondary objectives.

Additional exploratory analyses of the data will be conducted as deemed appropriate.

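### Should SAP 9.3.2 bar significance claims for AUC and Cmax ratios of insulin lispro to insulin aspart, since separate assays measure them?

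*SAP*

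**What the plan says.** SAP 9.3.2 analyses the time parameters (early and late 50% tmax, and tmax) in a mixed model with all four products, and takes significance from the p-value for the difference in LSmeans. For exposure it adds this on log-transformed AUCs and Cmax values: "for insulin lispro/aspart may be evaluated to estimate geometric means, ratios of geometric means and their corresponding 95% CIs using the same mixed-effect model" (the one used for the time parameters). It then says "Statistical significance will be achieved when the p-value for a test is less than 0.05". It names LY900014 versus Humalog as the primary comparison and lists three more: LY900014 versus FIASP, LY900014 versus NovoRapid, and Humalog versus NovoRapid. Protocol 10.3.2.2 has the same text. Protocol 10.3 sets the general level: "Unless otherwise noted, all tests of treatment effects will be conducted at a 2-sided alpha level of 0.05".

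On measurement, Protocol 9.5 plans "serum concentrations of insulin lispro and plasma or serum concentrations of insulin aspart in patients with T1DM". Protocol 9.5.1 gives each analyte its own specific method: "Serum concentrations of insulin lispro will be measured using a validated" method for lispro, and "Plasma or serum concentrations of insulin aspart in patients with T1DM will be measured using a validated" method for aspart. SAP 9.3.1 carries this through: "Serum insulin lispro and plasma or serum insulin aspart concentrations will be used to calculate several PK parameters". Protocol 5.4 also refers to separate assays, giving as the reason for choosing insulin glulisine that "it does not cross-react with either the insulin lispro- or insulin aspart-specific assay used for the PK analysis".

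In the objectives table (Protocol 4), early 50% tmax is the only endpoint for the four-product PK objective. AUC(0-30min) is a primary endpoint, but only for LY900014 against Humalog.

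**The concern.** All three additional contrasts set a lispro product against an aspart product. In each of them the assay, and possibly the matrix, changes with the product. Randomisation, blinding and the crossover cannot separate the two. If one method read systematically higher than the other, every AUC and Cmax ratio between analytes would carry that factor, which could create a product difference or hide one.

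The text does not clearly rule out significance claims here. The p<0.05 sentence comes directly after the AUC and Cmax sentence and directly before the list of contrasts, and no readable section warns about comparing concentrations across assays. Protocol 3.1 presents the study as a chance to compare these formulations under identical conditions, so a reader could take a significant AUC ratio as a property of the products. At stake is the interpretation of secondary PK output, not the primary comparison.

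**Working it through.** **Inputs.** 64 completers, two-sided alpha 0.05, and an SD of the within-subject difference on the log scale of 0.35 for AUC(0-30min) and 0.3 for early 50% tmax (SAP 7, Protocol 10.1). These SDs are stated for LY900014 versus Humalog. The documents give no SD for a lispro-aspart contrast and no assay offset, so both are assumed below.

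**The plan's own figures.** Power = Φ(|ln ratio| / (SD/√64) − 1.96).

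- Two-fold AUC(0-30min): ln 2 / (0.35/8) = 0.693/0.04375 = 15.8, power above 0.999. Stated: at least 95%.
- 35% reduction in early 50% tmax: 0.431/0.0375 = 11.5, power above 0.999. Stated: greater than 95%.
- 20% reduction against FIASP, assuming the 0.3 also applies: 0.223/0.0375 = 5.95, power 0.9999. Stated: more than 95%.

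All three are reproduced. The plan quantifies no power for insulin AUC or Cmax against an aspart product.

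**What an offset would do.** Suppose the true ratio is 1 and one assay reads higher by a factor b. The noncentrality is ln b / (SD/8). For b = 1.10 and SD 0.35 it is 0.0953/0.04375 = 2.18. The probability of p<0.05 (paired t, 63 df, noncentral t) is:

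| Assumed offset | SD 0.25 | SD 0.35 | SD 0.495 |
|---|---|---|---|
| 5% | 34% | 20% | 12% |
| 10% | 85% | 57% | 33% |
| 15% | 99% | 88% | 60% |
| 20% | 100% | 98% | 83% |

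The 0.495 is 0.35 × √2, in case 0.35 is really the SD of a single measurement. The 0.25 has no source in the documents and only widens the range. A simulated 64-patient balanced four-period crossover (4,000 runs per setting, SD 0.35) gave 0.047, 0.57 and 0.99 at offsets of 0%, 10% and 20%.

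Masking is the mirror image. For a true ratio of 1.20 at SD 0.35, power is 98%. An opposing 10% offset leaves ln 1.20 − ln 1.10 = 0.087, and 0.087/0.04375 = 1.99, so power is about 50%.

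**The listed cross-product endpoint.** A constant multiplier scales Cmax and half of Cmax alike, so the time at which half of Cmax is reached does not move. On an illustrative profile at the protocol's sampling times, a 1.2-fold scaling left early 50% tmax at 9.36 minutes and multiplied AUC by 1.2. This protection covers proportional offsets only, not non-linearity or different quantification limits.

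**The primary contrast.** LY900014 and Humalog share one analyte and one assay. In the simulation without a true difference, and with equal residual variances, their estimated log difference stayed at about 0 and rejection was 0.045 to 0.056 at every offset. One link remains: the model as described has a single residual variance, to which the aspart data contribute. If the aspart variance were twice that of lispro, the standard error would be √((1+2)/2) = 1.22 times too large. Type I error would fall to about 0.016, and power for the two-fold effect would stay above 0.999.

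**What a restriction would change.** The obvious remedy is to drop cross-analyte p-values and keep ratios with 95% CIs. In the same model a 95% CI excludes 1 exactly when p<0.05. At SD 0.35 the half-width is 1.998 × 0.35/8 = 0.0874 on the log scale, so an observed ratio outside about 0.916 to 1.091 is flagged either way. No estimate, interval, sample size or power figure changes.

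**The case for a change.** The best argument for an edit is that an estimation-only reading of the AUC sentence cannot be complete. The plan powers a test of AUC(0-30min) for LY900014 against Humalog, and the time parameters already have their own p-value sentence. The general p<0.05 rule is therefore what covers the primary AUC test. If it reaches AUC there, nothing in the wording stops it from reaching AUC in the contrasts listed beneath it. Validation of each method does not establish that the two agree. A clarification would take a few sentences and give up p-values that no listed endpoint needs.

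Much of this stands. The wording is ambiguous, assay and product are confounded in the three contrasts, and no readable section says so. Two things do not follow. First, the need to test AUC for LY900014 against Humalog is itself a good reason for a rule not confined to time parameters, so its generality is not a decision to make cross-analyte claims. Second, the calculations show sensitivity to an offset, not that one exists. Wording that leaves aspart in plasma or serum keeps the matrix open; it does not say the matrices differ. Without evidence of bias, reasonable statisticians would differ on giving up formal inference for these ratios.

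**Conclusion.** No change to the plan is needed. The gap concerns the interpretation of optional, secondary output: the AUC and Cmax analysis is permissive and framed as ratios with intervals, and the four-product PK objective rests on early 50% tmax. The documents do not show that following the plan gives a wrong result, and a restriction would leave every reported ratio and interval as it is.

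The 57% at a 10% offset, within a range of 12% to 100% over the grid, is illustrative. It assumes a proportional offset of unknown size, no true difference, and an SD borrowed from a lispro-lispro contrast. An analyst writing the study report can name the assay and matrix beside any cross-analyte AUC or Cmax ratio, and cite assay-comparability data if they exist, without amending the SAP. Evidence of a material offset between the two methods would be a reason to reconsider.
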